At the end of the program, a research team member will visit participants' home and evaluate the participants' perception and satisfaction for the program using a quantitative semi-structure interview. The interview will be recorded and transcribed for the qualitative analysis. Participants will be asked to complete the questionnaires. Participants' blood and sweat will be collected. The feasibility of the intervention program will be determined from the achievement of individual physical activity goal. At the end of 4 week program, research team will review the participants ability to achieve at least 75% of the individual's exercise goal (for example, if the goal is to exercise at the fat burn level (50-60% maximum heart rate measured by FitBit) for 30 min/day 3 days week, participants can exercise for 30 min for at least 2 days or FitBit data showed more than 60 active min). For this first phase, at least 50% of participants will need to meet 75% of personal goal in at least 2 weeks for the trial to continue onto phase II. For participants who do not achieve 75% of their individual exercise goal, the barriers will be identified that the weekly goals will be revised until the 75% of weekly personal exercise goals is met. If the feasibility threshold (less than 50% of participants achieve 75% of their weekly goals for 2 weeks) does not reach, we will adjust the goal setting process and recruit more participants. Moreover, we will descriptive information from the phase I to help inform alternative approaches to the anticipated analysis, sample size estimates for phase II, and additional key variables to be measured in phase II (intervention dose, fidelity, and additional process variables).

Intervention

Tailored Technology-Enhance Home-based Exercise Program:

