The tailored technology enhanced home-based exercise (iHBE) program is a 4-week program with 1 assessment home visit session, 4 home visits during exercise. The detail activities are presented in table 1. The technologies, a wearable device, and a smartphone application, will be used as a tool to monitor physical performance (heart rate, step count), provide immediate feedback, send daily reminding message through mEMA. The coded raw data without personal identification information from the wearable device will be sent to the servers where we can store it in the database alongside the mEMA data and create custom reports showing HR 30 minute before each EMA survey, showing HR and previous self-report responses before/ after each automatically triggered EMA.

Weeks	Program Activities
Assessment session (home visit; Week 0)	
A research team member (research nurses and/or physical therapist) will meet and assess the participants' perception of PA and goals. Participants will complete the questionnaires for baseline symptoms, Affective Well Being (AWB) and resilience. Participants' blood and sweat will be collected. The research team will help the participants to identify the barriers, prioritize goals for weekly activity and make a plan to achieve these goals. Participants will be asked the perception of their ability to complete the six-minute walk and their exertion level, then choose the PA modality, frequency, duration and time of the day of their exercise based on their preference, and goals.
 
Exercise intervention options
 
Option 1: The NIA Go4Life exercise
 
Option 2: Iyengar-style yoga 10-20 minutes on at least 2 days per week

Date: November 14, 2018

Principal Investigator: [name]

Application Number: IRB00175781

Weeks	Program Activities
	
Option 3: Walking to achieve the weekly goal (e.g., walk 5 min for 3 days/week and increase 1-2 min/week)
 
Option 4: Modified Otago exercise intervention
 
Participants will be trained to use the FitBit Charge 2 and mEMA application. During this home visit, participants will practice their selected exercise with a physical therapist or an RN, set the wearable device and record their HR, fatigue and pain level at the end of each exercise session on the mEMA. Participants will receive a booklet containing the information of their selected exercise intervention and a weekly planner.

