Primary objectives of this phase are to evaluate the feasibility and acceptability of the iBHE program. Eight participants who have completed treatment for a solid tumor cancer with at least one comorbidity (e.g., diabetes and/or hypertension) will be assigned to an open-label trial of the iBHE. At the completion of the program (4 weeks), the primary investigator will conduct a semi-structured interview to gather feedback on the program feasibility, goal setting, problem-solving strategies, exercise choices and tracking mechanisms, program feasibility, and acceptability. The interview will be recorded and transcribed verbatim.

The feasibility of the program

The feasibility of the intervention program will be determined from the achievement of individual physical activity goal. At the end of 4 week program, research team will review the participants ability to achieve at least 75% of the individual's exercise goal (for example, if the goal is to exercise at the fat burn level (50-60% maximum heart rate measured by FitBit) for 30 min/day 3 days week, participants can exercise for 30 min for at least 2 days or FitBit data showed more than 60 active min). For this first phase, at least 50% of participants will need to meet 75% of personal goal in at least 2 weeks for the trial to continue onto phase II. For participants who do not achieve 75% of their individual exercise goal, the barriers will be identified that the weekly goals will be revised until the 75% of weekly personal exercise goals is met. If the feasibility threshold (less than 50% of participants achieve 75% of their weekly goals for 2 weeks) does not reach, we will adjust the goal setting process and recruit more participants.

The feasibility of the recruitment will be determined by the number of screened participants, eligible participants and participants who refuse to be in the study and rational will be examined and recorded as indicator of feasibility. The feasibility of delivering the program will be evaluated by examining the number and timing for actual versus planned home visit and the duration of each visit. The intervention checklist will be filled by the research assistants for each home visit to assess the intervention content delivery.

The acceptability of the program

The acceptability of the program will be assessed using the semi-structure interview. The common feedback and suggestion for intervention during the semi-structure interview will be noted.

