Date: November 14, 2018

Principal Investigator: [name]

Application Number: IRB00175781

The compliance of the program

The compliance of this program will be monitored using active min and daily heart rate zone data from the wearable device (FitBit Charge 2). The weekly goals on number of day for physical activity and duration of the physical activity will be set. The number active min and duration of the heart rate in at least “Fat Burn” zone per day will be recorded for the duration of physical activity/day. The number of days the participant achieve the goals (duration and days) for physical activity will be used to measure the compliance of the program.

The descriptive information from the phase I to help inform alternative approaches to the anticipated analysis, sample size estimates for phase II, and additional key variables to be measured in phase II (intervention dose, fidelity, and additional process variables).

The program modification

Prior to phase 2, the primary investigator will discuss participants' feedback with the research teams.

The modification of exercise plan, wearable device, and phone application feature will be discussed until consensus program for each option is made.

8. Risks

Potential Risks:

The risks of participating in this study are minimal. Potential risks include

1. complications during the blood drawing for examples pain and bleeding at the drawing site.
2. complications during the sweat collection for examples rash, itching, redness and swollen.
3. minimum discomfort might occur during the wearable device (worn like a bracelet).
4. complications (e.g., fainting, injury) during the exercise program.

During the proposed study, if there is a serious adverse event, anticipated to be an uncommon occurrence, the PI will unmask treatment group assignment when necessary for the safety of the participant. The administration of the intervention may be discontinued at the participant's request or by the investigator, based on clinical judgment. Participants will be instructed to report any adverse event experienced after treatment without delay.

Adequacy of Protection against Risks: The safety of the study participants is essential. The primary investigator and research team will take all precautions to protect the participants against risks.

Protection against Risks: The principal investigator (PI) and research team plan to prevent the following risks:

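### The Phase 1 continuation rule requires at least 75% of the exercise goal, but its only worked example accepts about 67%

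*Combined protocol and SAP*

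**What the plan says.** Section 7 (Study Statistics, Phase 1), under the feasibility of the program, judges each participant at the end of the 4-week program on the "ability to achieve at least 75% of the individual's exercise goal". It gives one example: for a goal of 30 min a day on 3 days a week at the fat-burn heart rate, "participants can exercise for 30 min for at least 2 days or FitBit data showed more than 60 active min".

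The next sentence is the continuation rule: "at least 50% of participants will need to meet 75% of personal goal in at least 2 weeks for the trial to continue" to Phase 2. For those who fall short, barriers are identified and "the weekly goals will be revised until the 75% of weekly personal exercise goals is met". The text then describes a miss as "less than 50% of participants achieve 75% of their weekly goals for 2 weeks" and gives the consequence: "we will adjust the goal setting process and recruit more participants".

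Section 2 (Objectives) and the Phase 1 part of section 4 (Study Procedures) carry the same rule and the same example. No section gives a second worked example of the cut-off or says how a fractional number of days is rounded. Recruitment, delivery and acceptability are recorded or described without a numerical cut-off, so this is the only numerical condition for moving to Phase 2.

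**The concern.** The example is the one place where the plan shows how 75% becomes a pass or a fail on tracker data, and it does not show 75%. Staff who follow the percentage and staff who follow the example will classify some of the same weeks differently. The threshold feeds a count that needs 4 of 8 participants, so one differently classified person can decide whether the condition is met. The wording appears in three sections, so correcting one of them would leave the other two in conflict with it.

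**Working it through.** Inputs, all from section 7 (Phase 1) and repeated in sections 2 and 4: success is at least 75% of the individual goal; the example goal is 30 min on 3 days a week; the example accepts 30 min on at least 2 days, or more than 60 active min; at least 50% of participants must succeed in at least 2 weeks; there are 8 participants.

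1. Weekly goal in the example: 30 × 3 = 90 min.
2. The stated rule applied to that goal:
   - in minutes, 0.75 × 90 = 67.5 min;
   - in days, 0.75 × 3 = 2.25 days, so the smallest whole number of days that reaches 75% is 3.
3. What the example accepts:
   - days branch: 2/3 = 66.7%;
   - minutes branch: 60/90 = 66.7%, so any total just above that level passes.
4. Can the example be recovered from 75%?
   - Rounding 2.25 down, or to the nearest whole day, gives 2. That may be where the days branch came from, but 2 of 3 days is still 66.7%.
   - Applying 75% to each session gives 0.75 × 30 = 22.5 min, and 22.5 × 3 = 67.5 min, the same as in step 2.
   - None of these gives a cut-off of 60 min at 75%.
5. The gap: a week with exactly two 30-min sessions and nothing else (60 min, 66.7%), or with more than 60 but less than 67.5 active min, passes the example and fails the rule.
6. Effect on the continuation count: 0.50 × 8 = 4 participants are needed. As an illustration, assume that every goal is 90 min, that three participants reach 75% in two weeks, that a fourth falls in the gap in two weeks, and that the other four succeed under neither reading.
   - Under the 75% rule: 3/8 = 37.5%, not met.
   - Under the example: 4/8 = 50%, met.

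How often this would happen cannot be worked out from the documents, which give no distribution of weekly minutes, no spread and no correlation between weeks. The conflict in steps 1 to 5 does not depend on any of these.

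**The case against.** The strongest reply is that this is a parenthetical example in an eight-person open-label phase, that it probably reflects rounding 2.25 sessions to 2, and that little follows from it. Part of this stands. Rounding is a plausible origin, and a miss does not stop the study. It would also be wrong to infer that the count decides whether the intervention is reworked at all: the Phase 1 aim in section 2, the Phase 1 design text in section 4 and the program modification paragraph in section 7 all allow changes before Phase 2 whatever the result. What a miss adds is that goal setting must be adjusted and more participants recruited before continuing.

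Rounding does not remove the conflict, however. No rounding rule is stated, and minutes need none.

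The minutes branch may not be like for like, since the goal is time at a heart-rate level and the branch counts active minutes; the compliance paragraph of section 7 lists the two separately. The days branch, 2 of 3, is therefore the more secure evidence, and it is sufficient alone.

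Three stronger readings are tempting and are not supported:

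- That the example implies always rounding down, so that the yoga option in Table 1 ("Iyengar-style yoga 10-20 minutes on at least 2 days per week") could be passed with 1 of 2 days, or 50%. Rounding to the nearest day also turns 2.25 into 2, and with halves rounded up it turns 0.75 × 2 = 1.5 into 2 of 2 days. The documents do not say which applies.
- That the chance of continuing shifts by some large, known amount. Any such figure needs assumed weekly minutes and a common 90-min goal. Goals are individual, and the two readings separate mainly when typical attainment lies near the cut-offs.
- That revising missed goals makes the condition self-fulfilling. The plan does not say whether the original or the revised goal counts. Its reference to participants' weekly goals can be read as the goal in force that week. This is a missing detail and not evidence of a fault.

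**Conclusion.** Wrong as written. The stated threshold is at least 75%; the only illustration of it passes 66.7%, a shortfall of 8.3 percentage points (75 − 66.7), or 7.5 min on a 90-min goal (67.5 − 60). This follows from the plan's own figures without further assumptions. It can change the go/no-go count by one participant, from 3/8 to 4/8, under the illustrative results and common 90-min goal assumed above; the documents do not allow a statement of how likely that is. The consequence is limited to whether adjusted goal setting and added recruitment are required before continuing. It is still worth fixing, because no other numerical condition governs the step to Phase 2.

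**What to change.** Before Phase 1 is scored, reconcile the threshold and the example in section 2, section 4 (Phase 1) and section 7 (Phase 1), using identical wording in all three. Either make the example match 75% (67.5 min or, in whole days, 3 of 3) or state a two-thirds threshold and keep the example. This review takes no view on which is right. State how a fractional number of days is rounded, so that the rule works for goals other than 3 days a week.

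The cost is wording only. The one downside is that the reported feasibility rate may be slightly less favourable if the example is brought up to 75%.

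A lesser clarification, separate from the error: say whether the go/no-go count uses the original or the revised weekly goal. The compliance paragraph says "The weekly goals on number of day for physical activity and duration of the physical activity will be set", and one added sentence there or in the feasibility paragraph would settle it.

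### The Phase 1 gate to Phase 2 is scored on weekly goals that the same paragraph revises until they are met, so a pass does not separate adherence from lowered targets

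*Combined protocol and SAP*

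**What the plan says.** The rule is in the combined protocol and SAP, section 7 (Study Statistics, Phase 1), under the feasibility of the program. It is repeated in section 2 (Objectives) and section 4 (Study Procedures, Phase 1).

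- **Size of the phase.** Eight participants, open label, one arm, 4 weeks.
- **Gate.** "at least 50% of participants will need to meet 75% of personal goal in at least 2 weeks" for the trial to go on to Phase 2.
- **Revision.** For participants below 75%, "the barriers will be identified that the weekly goals will be revised until the 75% of weekly personal exercise goals is met".
- **Definition of a miss.** "less than 50% of participants achieve 75% of their weekly goals for 2 weeks".
- **Consequence of a miss.** "we will adjust the goal setting process and recruit more participants".

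Table 1 describes the week 0 visit, at which the team helps participants to "prioritize goals for weekly activity and make a plan to achieve these goals". Participants choose the type, frequency and duration of exercise themselves. Table 1 also has the team review performance and tailor the exercise at home visits in each of weeks 1 to 4. The compliance measure in section 7 counts the days on which these same goals are achieved.

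**The concern.** The text uses one term, weekly goals, both for what is scored and for what is revised. It does not fix the scoring goal at week 0, limit the number or size of revisions, or exclude weeks scored under a revised goal. If those weeks count, the denominator of the 75% can be lowered until the participant's existing activity reaches it.

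What is at stake is the decision to start a 50-person randomised phase. A pass should mean that low-income survivors with comorbidity can follow the programme they set out on. Under this rule it may mean only that targets were lowered to what they were already doing. The compliance measure has the same weakness because it uses the same goals.

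**Working it through.** **Plan's own figure.** The plan states no error rate, power or sample size justification for the Phase 1 gate, so there is nothing to reproduce. The alpha of .05 and power of 0.80 belong to Phase 2.

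**Inputs from section 7.** n = 8; the gate is 50% of 8 = 4 participants; each needs at least 2 of 4 weeks at 75% of goal.

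**Assumed inputs.** The weekly success probabilities are not in the documents and are shown as a range. Weeks and participants are treated as independent.

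**Step 1: how a revision can create a success.** The plan's example goal is 30 min on 3 days, or 90 min a week. Suppose a participant does 30 min a week throughout. Against 90 min this is 30/90 = 33%, a miss in weeks 1 and 2. If the goal is revised to 40 min (an illustrative figure), 30/40 = 75%, a success in weeks 3 and 4. The participant meets the 2-week rule with unchanged activity.

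**Step 2: participant-level success.** Let a be the success chance in weeks 1 and 2, and b the chance in weeks 3 and 4. Then

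P(at least 2 of 4) = 1 − (1−a)²(1−b)² − 2a(1−a)(1−b)² − 2b(1−b)(1−a)².

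For a = 0.2, b = 0.4: 1 − 0.2304 − 0.1152 − 0.3072 = 0.347.

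**Step 3: passing the gate.** P(pass) is the probability that a binomial count with n = 8 and the Step 2 probability is at least 4.

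| Weeks 1–2 (a) | Weeks 3–4 (b) | Participant succeeds | Gate passed |
|---|---|---|---|
| 0.2 | 0.2 (fixed goal) | 0.181 | 0.040 |
| 0.2 | 0.3 | 0.261 | 0.129 |
| 0.2 | 0.4 | 0.347 | 0.288 |
| 0.2 | 0.6 | 0.539 | 0.719 |
| 0.2 | 0.8 | 0.757 | 0.976 |
| 0.3 | 0.3 (fixed goal) | 0.348 | 0.290 |
| 0.3 | 0.6 | 0.619 | 0.855 |
| 0.3 | 0.8 | 0.807 | 0.991 |
| 0.4 | 0.4 (fixed goal) | 0.525 | 0.689 |
| 0.5 | 0.5 (fixed goal) | 0.688 | 0.932 |

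With fixed goals the gate discriminates: 4%, 29%, 69% and 93% at weekly success of 0.2, 0.3, 0.4 and 0.5. With revised goals the result depends mainly on how far the targets are lowered.

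**Step 4: repeat attempts.** After a miss the plan recruits more participants, without a limit. Even with fixed goals, one further cohort of 8 scored alone raises the chance of a pass at 0.3 from 0.290 to 1 − (1 − 0.290)² = 0.496.

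**Step 5: the 75% example.** Section 7 illustrates 75% of the 30 min, 3-day goal by 2 days or more than 60 active minutes. But 2/3 = 66.7% and 60/90 = 66.7%, whereas 75% is 0.75 × 3 = 2.25 days or 0.75 × 90 = 67.5 min. The criterion and its example disagree.

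**Step 6: precision.** Exactly 4 successes of 8 has an exact (Clopper-Pearson) 95% interval of 16% to 84%.

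**The case against.** The strongest reply is that the plan never says that weeks under a revised goal count. The sentence before the gate places the review at the end of the 4-week programme, so revision could follow that review and leave the score untouched. That reading is possible. It is less likely, because goals are weekly, tailoring takes place at the week 1 to 4 visits, revision continues until the goal is met, and the definition of a miss refers to weekly goals. Either way, the text must say which goal is scored.

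A second reply is that goal setting and tailoring are the intervention, so attainment after tailoring is a fair thing to measure. It is, as a descriptive result. It cannot also be the yardstick for a numerical gate if the yardstick has no floor.

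Three stronger inferences are tempting, and the documents do not support them:

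- **That the gate can hardly fail.** Two successful weeks of four are still needed, and drop-outs and non-exercisers can fail. With modest revision (0.2 rising to 0.4) the gate is passed only 29% of the time.
- **That Aim 1 is uninformative.** Section 7 also collects screening, eligibility and refusal counts, planned versus actual visits, a delivery checklist, interviews, and daily active minutes and heart-rate-zone time. None has a pass mark, but none depends on the goal, and the device data would show targets lowered to existing behaviour.
- **That a miss makes no difference.** It sends the team back to change goal setting and does not release Phase 2. What is missing is an end point to that loop.

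**Conclusion.** The point holds for the gate and for the compliance measure that shares its goals. On the likelier reading, a pass does not distinguish adherence from lowered targets, and no result is defined as a no-go. At an assumed weekly success of 0.2 against the original goal, revision could move the chance of a pass from 4% to between 29% and 98% for weeks 3 and 4 at 0.4 to 0.8. At 0.5 there is little left to inflate, since the fixed-goal rule already passes 93% of the time. These figures rest on assumed probabilities and independent weeks, and on revised weeks being counted.

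The randomised Phase 2 comparison and its analysis are not biased by this rule. In an eight-person formative phase this is something that should be fixed before Phase 1 results are used to release Phase 2. It is not a flaw that invalidates the study.

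**What to change.** In section 7, and in the repeated text of sections 2 and 4:

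1. Keep revising goals as coaching, but score the progression rule against the goal recorded at the week 0 visit, including any week-by-week increase planned at that visit. Table 1 gives a walking goal that rises each week, so scoring against the first week's level alone could make the test easier.
2. Count all enrolled participants, including drop-outs, in the denominator.
3. Report attainment of revised goals, and the size of each revision, as separate descriptive results. State which goal the compliance measure uses.
4. Apply the same rule to any added cohort alone, and state how many added cohorts are allowed before the programme is declared not feasible as designed.
5. Reconcile the 75% criterion with its 66.7% example.

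The cost is protocol wording: goals are set at week 0 and activity is measured daily by the device. The downside is a less favourable pass rate. Two limits remain. Week 0 goals are self-chosen, so a low first goal would still be easy to meet, and the initial goals should be reported. With 8 participants the gate also stays imprecise, as the interval for 4 of 8 shows, so it should be read with the other feasibility measures.
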